6.4 Secondary endpoint analysis

The secondary endpoints to be analysed is presented in Table 6.1 together with the outcome measure and methodology.

Table 6.1: Overview of outcome measures and methods of analysis to investigate secondary endpoints.

Variable/outcome	Outcome measure	Methods of analysis
1) Length of hospitalisation (LOS) during index stay	Days [continuous]	T-test, and potentially Anova
2) Time to first unplanned readmission within 12 months after discharge from index hospital stay	Days [continuous]	Kaplan Meier method and the log-rank test. Hazard ratios (HRs) with 95% confidence intervals will be estimated using a Cox proportional hazards model.
3) The proportion of patients readmitted acutely within 30 days	Proportion	Xhi-square test
4) 12-month mortality	Proportion	Total mortality will be analysed as a time-to-event analysis. The Kaplan Meier method and the log-rank test will be applied. Further, a Cox proportional HR model will be applied to estimate HRs. HRs will be presented with 95% confidence intervals.

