2.3 Secondary endpoints

Statistical analysis plan will be presented in this SAP only for the following secondary endpoints:

- Length of index hospital stay
- Time to first acute readmission after discharge from index hospital stay (12 months follow-up)
- The proportion of patients with acute readmissions within 30 days of discharge
- Mortality rate during 12 months' follow-up

Specification:

Some of the secondary endpoints from the protocol have been excluded from this SAP and will be presented in SAPs for follow-up studies.

3. Methods

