3.1 General Study Design and Plan

We will recruit eligible participants to the study when they are admitted to the geriatric internal medicines ward (hereby called geriatric ward) in Tromsø or the general internal medicines ward (hereby called medicine ward) in Harstad. Participants will be randomized into two study arms, intervention and control (standard care) in a 1:1 relationship, stratifying on study site only. Randomization is performed after eligibility has been confirmed and patients have consented to participate. Consecutively, the intervention is commenced.

Study progress:

- The study started including patients in Tromsø on 22. September 2016
- The study started including patients in Harstad on March 2017
- Inclusion stopped in December 2019 in both study sites. The last patient was discharged from hospital on 22. December 2019
- Patients are followed-up for 12 months after discharge, and data will be collected after December 2020

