5.1 Patient flow

The CONSORT flow diagram for the Patient flow will be developed, see Figure 5.1 below for a draft. Numbers that remain to be established: 1) Patients admitted to the hospital wards during study period, 2) Patients meeting the inclusion criteria, 3) Patients excluded and reasons why, 4) Patients dying during hospitalisation, 5) Patients dying during follow-up, 6) Patients lost to follow-up, 7) Patients in intention-to-treat analysis (ITT).

[figure not shown]

Figure 5.1 Participant flow diagram

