6.3 Primary endpoint analysis

The composite endpoint

The primary endpoint is defined as the composite endpoint “acute readmission and ED visits” 12 months after discharge from the index hospital stay in the intervention group compared with the control group. Consequently, the endpoint comprises both “readmissions” and “visit to emergency departments (ED)”.

Hypothesis

- The H0 hypothesis is: The intervention does not influence the number of primary endpoints during 12 months after index hospitalization.
- The H1 hypothesis is: The intervention influences the number of primary endpoints during 12 months after index hospitalization.

Figure 6.2 illustrates how we assume that the endpoint will occur during the follow-up time.

[figure not shown]

Figure 6.2: Illustrations of primary endpoints during a 12-month follow-up time for patients in the two groups, assuming that we will see a difference between the groups.

- a) Number of patients having 1-x number of endpoints during the 12-month follow-up period.
- b) Cumulative number of endpoints (in total) 1-12 months after index hospital discharge.

Person-time (time under risk for experiencing an endpoint) contribution

Each patient may experience many endpoints during the 12-month follow-up, and the primary endpoint per patient will be related to the patient’s person-time contribution during the 12-month follow-up period after index hospital discharge.

To account for that a new endpoint cannot occur in the period a patient is “in an endpoint” (i.e. time in hospital if patient is hospitalised), and that patients may die before the end of the 12-month follow-up period, we will calculate person-time contribution for all patients, which is “time outside hospital” in the follow-up period where the person is still alive. Consequently, total person time contribution per patient =

365 days follow-up time after hospital discharge, minus “time in an endpoint” minus time after (potential) death.

Primary endpoint analysis

Specification

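### Table 6.1 sets no rule for death before first readmission and no time origin for mortality; the default readings overstate absolute readmission risk and leave in-hospital deaths uncounted

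*SAP*

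**What the plan says.** Two rows of SAP Table 6.1 (section 6.4) are time-to-event analyses.

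- **Row 2** is "Time to first unplanned readmission within 12 months after discharge from index hospital stay". The clock starts at discharge, and the methods are "Kaplan Meier method and the log-rank test. Hazard ratios (HRs) with 95% confidence intervals will be estimated using a Cox proportional hazards model". Neither the row nor the text around it says what happens to a patient who dies before any readmission.
- **Row 4** is 12-month mortality. The outcome measure is given as a proportion, but the method column says "Total mortality will be analysed as a time-to-event analysis". No starting point is given.

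Elsewhere the SAP shows that both matters were in view. Section 6.3 notes, for the primary endpoint, that "patients may die before the end of the 12-month follow-up period" and takes time after death out of the person-time. Section 2.3 words the mortality endpoint as "Mortality rate during 12 months' follow-up", and section 3.1 says "Patients are followed-up for 12 months after discharge". Section 3.1 also places randomisation after consent, during the index stay, with the intervention starting next. Section 5.1 lists "Patients dying during hospitalisation" as one count for the flow diagram and deaths during follow-up as a separate one.

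**The concern.** The patients are aged 70 or over and acutely admitted, so death within a year is common enough to be a secondary endpoint itself. A patient who dies cannot then be readmitted. Kaplan-Meier with death censored estimates the readmission risk as if nobody died, which is higher than the share of patients actually readmitted. If mortality differs between the arms, the overstatement differs too. Row 3 reports 30-day readmission as a plain proportion, so a Kaplan-Meier curve read at day 30 could disagree with the trial's own 30-day figure.

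For mortality, the intervention begins in hospital. A clock that starts at discharge conditions on surviving to discharge, which happens after randomisation. An in-hospital benefit or harm would then not appear in the endpoint.

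Section 4.6 treats the secondary outcomes as confirmatory, so neither choice should be left until the data are in hand.

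**Working it through.** The SAP gives no readmission or mortality rate for these two endpoints, so there is no planned figure to reproduce. All rates below are assumptions, shown as ranges.

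**First readmission.** Assume constant hazards over one year: *h* for first readmission and *d* for death before readmission.

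- Censoring deaths: 1 − KM = 1 − exp(−h)
- Death as a competing event: CIF = h/(h+d) × [1 − exp(−(h+d))]

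Worked case: 1 − KM = 50% gives h = −ln(0.5) = 0.693. A net death risk of 20% gives d = −ln(0.8) = 0.223. Then CIF = 0.693/0.916 × (1 − 0.40) = 45.4%, so the overstatement is 4.6 points.

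| Assumption | 1 − KM | CIF | Overstatement (points) |
|---|---|---|---|
| 1 − KM 40%, net death 10% | 40.0% | 38.1% | 1.9 |
| 1 − KM 50%, net death 20% | 50.0% | 45.4% | 4.6 |
| 1 − KM 60%, net death 30% | 60.0% | 51.8% | 8.2 |
| h = 0.7, d = 0.20 | 50.3% | 46.2% | 4.2 |
| h = 1.0, d = 0.30 | 63.2% | 56.0% | 7.3 |
| h = 1.2, d = 0.35 | 69.9% | 61.0% | 8.9 |
| h = 1.0, d = 0.15 | 63.2% | 59.4% | 3.8 |
| h = 1.0, d = 0.10 | 63.2% | 60.6% | 2.6 |

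The last two rows matter because *d* is the hazard of death *before* readmission. Total 12-month mortality may be much higher than *d* implies if deaths cluster after a readmission, and the overstatement is then smaller.

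**Hazard comparison.** Take the same *h* in both arms (1 − KM = 50%, cause-specific hazard ratio 1) and net death risks of 20% and 30%. The cumulative incidences are 45.4% and 42.9%. The hazard ratio is not biased by censoring deaths in this way, but it answers a different question from the cumulative risk.

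**Mortality origin.** Three steps, each from the SAP:

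1. The endpoint covers deaths during 12 months' follow-up (2.3).
2. The only definition of follow-up runs from discharge (3.1).
3. Deaths in hospital are listed apart from deaths during follow-up (5.1).

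Together these leave a patient who is randomised and dies before discharge outside the endpoint.

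For the size, let *p* be the assumed in-hospital death risk after randomisation and *m* the assumed 12-month mortality after discharge. The share of all deaths that is missed is p / [p + (1 − p)m].

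- p = 1%, m = 30%: 0.010 / (0.010 + 0.297) = 3.3%
- p = 5%, m = 20%: 0.050 / (0.050 + 0.190) = 20.8%

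With 500 patients (250 per arm, section 3.4), p of 1 to 5% is 5 to 25 deaths.

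**The case against.** The strongest reply is that the SAP is silent rather than wrong. It nowhere states that death is censored, and nowhere that the mortality clock starts at discharge. Row 2 names discharge; the mortality items do not. Both points stand, and the finding is therefore one of missing rules whose defaults are poor.

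A reader might infer that the log-rank test and hazard ratio for readmission are invalid. They are not: with deaths censored, both validly compare cause-specific hazards. Nor does row 2 promise a 12-month readmission probability. The problem is confined to the Kaplan-Meier curve, and arises as soon as that curve is read as a risk.

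A reader might also infer that the mortality analysis is restricted by design to patients who left hospital alive. The documents do not support that. The full analysis population in 4.2 and the exclusions in 6.2 do not remove in-hospital deaths, and 5.1 plans to count them. Figures 5.1 and 6.1 might show where these patients go, but they were not available for this review. What remains is that the available text does not place these deaths in the endpoint, and its definitions point away from including them.

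Finally, the sizes rest on assumed rates. Section 3.2 excludes patients judged terminally ill or with short life expectancy, which argues for the lower end of the ranges.

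**Conclusion.** The point holds as a gap in specification on two secondary endpoints.

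- **First readmission:** under the default of censoring at death, one minus Kaplan-Meier overstates absolute risk. The direction is certain whenever some patients die before readmission. The size, about 2 to 9 percentage points, assumes constant hazards and the ranges shown, and is smaller if most deaths follow a readmission. The hazard ratio and log-rank test are unaffected as cause-specific comparisons.
- **Mortality:** a discharge origin is the natural reading, not a stated rule. Under it, in-hospital deaths after randomisation fall outside the endpoint. The number cannot be known from the SAP; about 3 to 21% of deaths follows from assuming 1 to 5% in-hospital death and 20 to 30% mortality after discharge.

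Neither part touches the primary analysis. Both should be settled before unblinded results are seen.

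**What to change.** **Table 6.1, row 2.** Present the cumulative incidence function for first readmission, with death as a competing event, in place of the one-minus-Kaplan-Meier curve. Keep the log-rank test and the Cox model, state that death before readmission is censored in them, and label both as cause-specific. Gray's test may be added as an optional supplement; it tests a different hypothesis and need not replace log-rank.

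**Table 6.1, row 4.** State that all deaths from the date of randomisation to 12 months after it are counted, including deaths in hospital, in the full analysis population by assigned arm. Give the discharge-based result as a sensitivity analysis. Make section 2.3 agree.

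**Cost.** A few lines of SAP text and a little extra analysis. The cumulative incidence may need software other than SPSS, the only package named in 6.1. Times of death are already planned from the cause-of-death registry (4.3). Because randomisation precedes discharge, the planned follow-up to 12 months after discharge already covers 12 months after randomisation. The randomisation date is not listed in Appendix 1 and must be taken from the randomisation database, which that appendix already names as a source for study site.

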3.3 Randomisation and Blinding

Patients were randomized into intervention group and control group in a 1:1 relationship, only stratifying on study site. We applied block randomization with concealed and permuted randomization block sizes. The web-based randomization program was supplied by Unit for Applied Clinical Research, Faculty of Medicine Norwegian University of Science and Technology, Trondheim, which is an independent collaboration partner not involved in the project. Blinding was not feasible in this study, as everybody knew whether or not the intervention was delivered.

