4.5 Multi-centre Studies

The study sites in Tromsø and Harstad will be analysed together, but a subgroup analysis will be performed to investigate a possible centre effect. Regarding the intervention, the procedures, guidelines and working tools have been similar in both study sites and patients in the two study sites have been treated similarly. The only exception is with regard to collection of health-related quality of life. For this variable at baseline, all patients at study site Harstad were interviewed over telephone while for the Tromsø population, the first measurement was performed face-to-face.

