6.1 General on statistics

We will investigate data for normality and apply the appropriate statistical tests. A two-sided 5% significance level will be applied, with no adjustments for multiplicity.

All analyses will be performed applying SPSS for windows or Mac. P-values < 0.05 will be regarded as statistically significant. P-values ≥ 0.001 will be reported to 3 decimal places; p-values less than 0.001 will be reported as "<0.001". The mean, standard deviation, and any other statistics other than quantiles, will be reported to one decimal place greater than the original data. Quantiles, such as median, or minimum and maximum will use the same number of decimal places as the original data. Estimated parameters, not on the same scale as raw observations (e.g. regression coefficients) will be reported to 3 significant figures.

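### 30-day readmission is tested with a chi-square that ignores the site stratum, and no effect estimate with a confidence interval is planned

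*SAP*

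**What the plan says.** - **Endpoint.** SAP 2.3 lists "The proportion of patients with acute readmissions within 30 days of discharge". SAP 4.6 places secondary outcomes under confirmatory testing. SAP 6.1 adds: "A two-sided 5% significance level will be applied, with no adjustments for multiplicity".
- **Method.** In Table 6.1 (SAP 6.4), row 3, "The proportion of patients readmitted acutely within 30 days", has a proportion as outcome measure and "Xhi-square test" as the method, with nothing further.
- **Neighbouring rows.** For time to first readmission, row 2 says: "Hazard ratios (HRs) with 95% confidence intervals will be estimated using a Cox proportional hazards model". Row 4 (12-month mortality) makes the same commitment. SAP 6.1 sets rules for p-values and decimals but no general rule on effect estimates or intervals.
- **Randomisation.** SAP 3.3: "Patients were randomized into intervention group and control group in a 1:1 relationship, only stratifying on study site". SAP 1 describes a geriatric ward in Tromsø and a general internal medicine ward in Harstad.
- **Site in the analysis.** SAP 4.5 says the sites "will be analysed together, but a subgroup analysis will be performed to investigate a possible centre effect". SAP 4.3 lists site as subgroup 9.
- **Death.** For the primary endpoint, SAP 6.3 removes the time after death from person-time. For the 30-day proportion no rule is stated. SAP 6.2 does not list death among the reasons for exclusion from the intention-to-treat analysis, and SAP 5.1 counts deaths separately from loss to follow-up.

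**The concern.** Stratified randomisation balances the arms within each site. If readmission risk differs between the two wards, an analysis that ignores site leaves the between-site variation in the error term and gives up some of that precision.

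The missing estimate matters more to a reader. A test result alone does not show which differences the data rule out, and the same table provides that information for two other endpoints.

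Silence about death leaves the meaning of the proportion open. A patient who dies unreadmitted soon after discharge can no longer be readmitted. On the endpoint as worded, that patient remains in the denominator as not readmitted.

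**Working it through.** The SAP gives no 30-day readmission rate, no 30-day death rate and no split of patients between sites, so there is no plan figure to reproduce for this endpoint. The only input from the SAP is the target of 250 patients per arm (SAP 3.4). All rates below are assumptions.

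**1. Variance overstated by pooling.** Let a share w of patients be at a site with risk p1 and the rest at a site with risk p2, with overall risk p. Then

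p(1 − p) = [w·p1(1 − p1) + (1 − w)·p2(1 − p2)] + w(1 − w)(p1 − p2)²

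The chi-square uses the left side. Under stratified randomisation, the bracketed within-site term is the relevant one. With w = 0.5 and p = 20%:

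| Site risks | Pooled | Within-site | Excess |
|---|---|---|---|
| 18% / 22% | 0.1600 | (0.1476 + 0.1716)/2 = 0.1596 | 0.0004/0.1596 = 0.3% |
| 15% / 25% | 0.1600 | (0.1275 + 0.1875)/2 = 0.1575 | 0.0025/0.1575 = 1.6% |
| 12% / 28% | 0.1600 | (0.1056 + 0.2016)/2 = 0.1536 | 0.0064/0.1536 = 4.2% |

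**2. Unequal sites.** The excess term w(1 − w)(p1 − p2)² is largest at w = 0.5. At 70/30 the factor falls from 0.25 to 0.21, so for 12%/28% the excess falls from 0.0064 to 0.21 × 0.0256 = 0.0054. As a percentage it also depends on which site is larger:
- larger site at 28%: 0.0054/(0.7 × 0.2016 + 0.3 × 0.1056) = 0.0054/0.1728 = 3.1%
- larger site at 12%: 0.0054/(0.7 × 0.1056 + 0.3 × 0.2016) = 0.0054/0.1344 = 4.0%

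In absolute terms, unequal sites always reduce the overstatement. The percentage stays of the same order, and under mild imbalance it can sit a shade higher: at 60/40 with the larger site at 12%, 0.0061/0.1440 = 4.3%.

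**3. Effect on the test.** Simulation with 40,000 runs per scenario, 250 per arm and 125 per arm at each site:

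| Site risks | Type I error: chi-square / stratified | Power at odds ratio 0.5: chi-square / stratified |
|---|---|---|
| 20% / 20% | 0.047 / 0.047 | 78.7% / 78.7% |
| 25% / 15% | 0.047 / 0.049 | 78.3% / 78.5% |
| 30% / 10% | 0.043 / 0.050 | 75.6% / 77.2% |

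The chi-square never exceeds its nominal level. It loses between 0 and about 1.6 points of power, the latter only at the widest gap between sites.

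**4. What the missing interval would show.** The 95% half-width for a risk difference is 1.96 × √(2p(1 − p)/250). At p = 10%, 20% and 30% this is 5.3, 7.0 and 8.0 percentage points. A non-significant result would thus be compatible with differences of several points in either direction.

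**5. Death before readmission.** Assume a 20% readmission risk among patients who do not die first, and let d be the proportion who die unreadmitted within 30 days. The plain proportion is 0.20(1 − d); readmission or death is 0.20(1 − d) + d.

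| d, control / intervention | Plain proportion | Readmission or death |
|---|---|---|
| 5% / 5% | 19.0% / 19.0% | 24.0% / 24.0% |
| 5% / 8% | 19.0% / 18.4% | 24.0% / 26.4% |
| 5% / 10% | 19.0% / 18.0% | 24.0% / 28.0% |

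With equal early mortality there is no distortion. With more early deaths on intervention, the plain proportion leans 0.6 or 1.0 points towards intervention while the combined outcome points the other way.

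**The case against.** The strongest reply is that nothing here is an error. An unstratified chi-square is a legitimate test, and the SAP does not overlook site: it chooses to pool the sites and to examine site as a subgroup. That stands as far as validity goes. A reader might infer that ignoring the stratum makes the test invalid or too liberal; the simulation shows the opposite. A subgroup analysis does not, however, put site into the main comparison. That the two wards differ in readmission risk is plausible, but the SAP does not document it.

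A reader might also infer that the SAP classes patients who die unreadmitted as successes. No section says so. It follows by default from the endpoint definition and the list of exclusions, and is a gap rather than a rule. Three points limit it further: row 4 analyses mortality, so a material imbalance over 12 months would be visible; SAP 3.2 excludes patients judged terminally ill or with short life expectancy; and the plain proportion readmitted is a definable quantity in its own right.

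Finally, it would go too far to say that only a p-value will be reported. The outcome measure is a proportion, so arm-level proportions can be expected, and with the group sizes a reader could work out an interval. What stands is that the SAP commits to no effect measure and no interval here, and does so in the rows beside it.

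**Conclusion.** The point holds as a minor improvement to one secondary endpoint. Row 3 does not use the randomisation stratum and, unlike rows 2 and 4, promises no effect estimate with a confidence interval. The planned test is valid and at most slightly conservative. The variance overstatement of about 0.3% to 4% rests on assumed site risks and equal site sizes, and the absolute excess shrinks if the sites are unequal. The lack of an estimate is the more useful part to repair.

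On death, the documents support only that its handling is unspecified. The default treatment distorts the comparison only if early unreadmitted deaths differ between the arms, and nothing in the SAP indicates that they do.

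**What to change.** In Table 6.1, row 3:

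- Replace the chi-square with a Cochran-Mantel-Haenszel test stratified by site, and report the site-stratified risk difference with a 95% confidence interval beside the arm proportions.
- State how a patient who dies before any readmission within 30 days is counted, and report acute readmission or death within 30 days as a sensitivity analysis.
- Name the denominator. If it is patients discharged alive, show in-hospital deaths by arm: the intervention starts after randomisation during the index stay (SAP 3.1), so surviving to discharge is a post-randomisation event.
- Optionally, stratify the log-rank and Cox analyses in rows 2 and 4 by site for consistency.

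The cost is a few lines of SAP text. Site is already recorded (Appendix 1), and admissions and time of death come from the registries in SAP 4.3. The stratified risk difference can be computed from two 2 × 2 tables. The SAP is dated March 2021 and expects analysis in May–June 2021, so the change fits before the allocation code is revealed; made later, it should be labelled as such.
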